**Option 2**

**Describe how your study meets these criteria:**

a) The research presents no more than minimal risk to the participant:

Addition of the SAAF online survey does not alter or increase the risk to the participants.

b) Involves no procedures for which written consent is normally required outside of the research context (i.e. a cover letter on a survey, or a phone script):

Informed consent regarding continued contact with participations via email communication was obtained during initial consenting of this study. Addition of the SAAF will be accompanied with a cover letter and completion of the assessment will indicate implied consent.

**Option 3**

**Describe how your study meets these criteria:**

a) The subject (or legally authorized representative) is a member of a distinct cultural group or community in which signing forms is not the norm:

b) The research presents no more than minimal risk to the subject:

c) There is an appropriate alternative mechanism for documenting that informed consent was obtained:

61291  
CLOSED

## STUDY PERSONNEL

Do you have study personnel who will be assisting with the research?

After selecting 'Yes' or 'No' you must click the 'Save Study Personnel Information' button. [?](#)

Yes  No

## RESEARCH DESCRIPTION

1 unresolved  
comment(s)

You may attach a sponsor's protocol pages in the "Additional Information" section and refer to them where necessary in the Research Description. However, each prompt that applies to your study should contain at least a summary paragraph.

\*\*!!!PLEASE READ!!!\*\* Known Issue: The below text boxes do not allow symbols, web addresses, or special characters (characters on a standard keyboard should be ok). If something is entered that the text boxes don't allow, user will lose unsaved information.

**Workaround(s):**

- Save your work often to avoid losing data.
- Use one of the attachment buttons in this section, or under the Additional Information section to include the information with your application. During the document upload process, you will be able to provide a brief description of the attachment.

**Background:** Provide an introduction and background information. Describe past experimental and/or clinical findings leading to the formulation of your study. For research involving investigational drugs, describe the previously conducted animal and human studies. You may reference grant application/sponsor's relevant protocol pages and attach as an appendix in the E-IRB "Additional Information" section, however, a summary paragraph must be provided in the text box below. For research that involves FDA approved drugs or devices, describe the FDA approved uses of this drug/device in relation to your protocol. Attach a copy of the approved labeling as a product package insert or from the Physician's Desk Reference in the applicable E-IRB "Study Drug" or "Study Device" section.

Individuals with Alzheimer's disease and related dementias (ADRD) face numerous changes throughout the course of cognitive decline. Behaviors and psychiatric symptoms of dementia (BPSD) are reported in over 80% of those diagnosed with ADRD and contribute to increased mortality. Most common BPSD include apathy, depression, agitation, aggression, anxiety, and sleep disorders. These behaviors are often correlated with increased caregiver burden, placement in institutional care, and decreased quality of life for the caregiver and person with ADRD. Safe and effective treatment options are limited. Innovative intervention approaches for BPSD in persons with ADRD is needed and can be applied immediately.

National and international agencies in ADRD intervention recognize the need for non-pharmacological intervention, including environmental assessment and modification, as first-line treatment for BPSD in ADRD. However, lack of frameworks and protocols to guide and apply such intervention severely limit real-world implementation. Studies in ADRD research have examined interventions using fragments of the environment, such as physical modifications, caregiver training to improve social contexts, and sensory-based interventions, but there is limited representation in the evidence exploring holistic environmental design combining these aspects for optimal behavioral regulation and performance. There is significant need to establish innovative protocols for holistic environmental design as a well-defined first-line intervention for BPSD.

Recent evidence suggests similar behavioral sequelae between autism spectrum disorder (ASD), a neurodevelopmental disorder recognized in early childhood, and ADRD, neurodegenerative conditions at the opposite end of the life spectrum. The neurological overlap to cause similar behaviors is unknown at this time. Yet, interventions including pharmacological and non-pharmacological treatment are being shared between conditions. ASD is frequently treated with non-pharmacological approaches including environmental modification, sensory-based intervention, caregiver training, behavior therapy, and compensatory training. Currently, there is minimal evidence exploring non-pharmacological approaches derived from ASD treatment for behavioral management and regulation in those with ADRD.

Environmental design incorporates aspects of well-established ASD interventions including environmental modification, sensory-based intervention, and caregiver training to create ideal physical, social, and sensorial surroundings. Renowned gerontologists have long recognized behavior as a product of environmental interaction. In 1936, Kurt Lewin defined (B)ehavior as a (f)unction of the (P)erson and (E)nvironment:  $B = f(P, E)$ . Lawton and Nahemow developed the Ecological Model of Aging which depicts zones of adaptive behavior when environmental demands are attuned with one's competencies. By incorporating successful facets of interventions for similar ASD behaviors and increasingly recognized non-pharmacological interventions in ADRD care, environmental design protocols will create ideal surroundings for maximal function and adaptive behavioral response.

Maladaptive behaviors and BPSD can sometimes be attributed to environmental incongruence with the individuals' sensory needs, as defined in environmental press theory. Our environment is perceived through our senses. Additional physiological changes associated to aging such as sensory receptor changes and the onset of apathy in dementia can lead to internal causes of sensory deprivation. Under-stimulating environments can lead to external sensory deprivation possibly causing boredom, whereby eliciting maladaptive behaviors. Sensory processing theories, as defined by Dunn indicate sensory patterns and needs specific to each individual (Table 1). These sensory needs depict thresholds for optimal function of the nervous system. When paired with environmental stimuli, the result is behavioral expression. If demands of the environment are not compatible with sensory processing abilities, then the individual may not behave optimally. An environmental (physical and social) and behavioral, nonpharmacological approach may be most effective in promoting ideal sensory experiences whereby decreasing BPSD. Sensory-based assessment is necessary in determining individual sensory needs. The Adult sensory profile is a validated measure in those with dementia.

Current research lacks sensory-based assessment, individualization of intervention, use of protocols, and is plagued with methodological errors creating mixed results. Individual sensory programs, also known as sensory diets, have been shown effective for decreasing agitation in various neurological disorders, but have not been well-established with individual assessment, development and implementation in dementia care. Once established, environmental design protocols for ADRD care will likely decrease burdensome BPSD, decrease need for institutional care, and possibly delay mortality while preserving quality of

life.43 The need for well-designed non-pharmacological interventions for BPSD is significant.44 Application of the described here is driven by clinical observations across the lifespan and can have immediate translation into treatment options for BPSD.

**Objectives:** List your research objectives. You may reference grant application/sponsor's relevant protocol pages and attach as an appendix in the E-IRB "Additional Information" section, however, a summary paragraph must be provided in the text box below.

1. To assess feasibility of environmental design protocols for intervention adherence and behavior change in subjects with moderate to severe dementia.
2. To evaluate sensory processing patterns and preferences of subjects with moderate to severe dementia.
3. To assess behavioral impact of environmental design intervention on functional activity engagement and cognition.

**Study Design:** Describe the study design (e.g., single/double blind, parallel, crossover, etc.). Indicate whether or not the subjects will receive placebo medication at some point in the research procedures. Also, indicate whether or not the subjects will be randomized in this study. You may reference sponsor's protocol pages and attach as an appendix in the E-IRB "Additional Information" section, however, a summary paragraph must be provided in the text box below. (Including the study design table from a sponsor's protocol is helpful to IRB members.)

**Community-Based Participatory Research:** If you are conducting [community-based participatory research \(CBPR\)](#), describe strategies for involvement of community members in the design and implementation of the study, and dissemination of results from the study.

**Research Repositories:** If the purpose of this submission is to establish a Research Repository (bank, registry) indicate whether the material you plan to collect would or would not be available from a commercial supplier, clinical lab, or established IRB approved research repository. Provide scientific justification for establishment of an additional repository collecting duplicate material. Describe the repository design and operating procedures. For relevant information to include, see the [UK Research Biospecimen Bank Guidance](#) or the [UK Research Registry Guidance](#).

This study will use a single-blind, placebo controlled, three-arm, parallel-design. Thirty subjects with moderate to severe Alzheimer's disease as primary dementia type (Clinical Dementia Rating Scale score of 2-3) will be randomly assigned to one of three arms: standard care; standard protocol (pre-determined set of environmental design modifications); or personalized protocol (environmental design modification developed with subject based on sensory preference and behavioral needs). Intervention will last 4 weeks. Weekly monitoring for protocol adherence and adverse events will occur throughout study. An follow-up 4 weeks post-intervention will occur. The entire project will be conducted over 10 weeks of participant engagement.

With recent in-person limitations to due COVID-19, as well as the need for increased evidence involving telemedicine, this study will be conducted in accordance with the University of Kentucky Telemedicine regulations and practices. The University of Kentucky has had an active telehealth program since 1995 and has conducted hundreds of thousands of telehealth encounters using interactive videoconference technology in over 25 medical, surgical, mental/behavioral health and therapeutic specialties. UK's videoconference platform is Zoom. UK has a Business Associate Agreement with Zoom, and uses the HIPAA compliant version of the technology to insure patient confidentiality is maintained. Telehealth has proven to be a successful modality for clinical encounters for many years, but the COVID 19 pandemic crisis has escalated the use of telehealth at UK. The state of Kentucky shutdown of all elective medical services and the inherent fear of patients to come to a healthcare facility mandated that UK Healthcare launch an enterprise-wide telehealth solution to meet the overwhelming demand for acute primary care visits as well as scheduled visits that could not take place while clinics were closed. This new direct-to-consumer telehealth service that uses the patient's personal device (home computer, tablet or smartphone) is being used by over 15,000 patients/month.

Participants will be selected with assistance from Sanders Brown Center on Aging (SBCoA) staff using the University of Kentucky Alzheimer's Center Longitudinal participant database (IRB# 88-0102-F2L [[name], PI]). University of Kentucky Alzheimer's Disease Center Clinical Core Leader, [name], has approved access to and use of the University of Kentucky Alzheimer's Disease Center Community Registry database, which is located at the SBCoA Clinic, [name]. The database follows 200-300 volunteers who live in the local community around SBCoA Clinic for longitudinal data collection purposes. Participants with cognitive impairment are primary targets for data tracking for the database. Each participant in the database has corresponding information for primary caregivers, which is also maintained in the database. All cognitively impaired database enrollees and their caregivers have agreed to be contacted by SBCoA associates for invitation to participate in additional research projects. Annual confirmation is obtained by the center to ensure participants continue to permit contact via phone calls or other methods from researchers and staff at SBCoA for notification, explanation, and invitation to additional research opportunities offered by the University of Kentucky.

Patients of the Kentucky Neuroscience Institute with memory impairment may also be contacted for participation of this study. Upon identification of eligible participants, the KNI medical team will determine patient interest to be contacted by study personnel and notify [name] (PI) to follow up with contact to potential participants and/or the study flyer will be mailed or emailed to eligible patients with request to contact study personnel if interested in study participation.

Primary measures:

Feasibility will be assessed by monitoring of protocol adherence and behavior change.

- Caregivers will be responsible for providing treatment protocols throughout duration of treatment window. Adherence to the protocol will be kept and measured using the behavioral journal and intervention adherence log
- Weekly check-ins with the caregivers will provide opportunity to review adherence and reactions to the protocol, as well as assess for adverse reactions, need for modification, or discontinuation. If the investigator finds that the participant is noncompliant, the PI

may remove the participant from further participation in the study.

- Caregiver burden will be measured using the Zarit Caregiver Burden Scale.

Secondary measures:

- Behavior will be assessed using the Vineland Adaptive Behavior Scales (VABS) and the Neuropsychiatric Inventory (NPI) at baseline and post-intervention, and behavior tracking throughout intervention.
- Cognitive measures will include the MOCA and CDR at baseline, post-intervention and follow up
- Heart rate tracking and sleep will be measured using wearable activity tracker (Actigraph) at all times except while charging device.

Sensory processing patterns and functional activity engagement will be assessed for all participants with dementia and used for individualization arm of intervention.

- Sensory processing will be measured using the Adult Sensory Profile (ASP) for all subjects at baseline.
- Functional activity engagement will be measured using the Canadian Occupational Performance Measure (COPM) at baseline and post-intervention.

**Control Group:** Standard of care for behavioral management and 2-page educational pamphlet describing safety for home environments. At the conclusion of the study, following the four-week follow up visit, participants will be offered a standardized sensory kit (as described below) to use at their discretion.

**Standard Environmental Design Protocol:** Participants' caregivers will receive standard recommendations for physical environmental modifications, caregiving techniques, and a sensorimotor stimulation kit via mailing from study site. Physical environmental modifications will include declutter living space, reduce background noise, increase natural light, accommodate for accessibility to commode and areas for drinking and eating. Caregiving techniques will include training for calming demeanor (emotional contagion), needs-driven care to decrease onset of behavioral disruption, and accepting and accommodating approach to behavioral disruption. A sensorimotor stimulation kit will be provided to each participants' caregiver for administration three times per day, lasting 30-60 minutes total per day. The stimulation kit will include an item for tactile tool via hands and arms, auditory input via a CD or audio file for music and speakers, olfactory input will be gained through use of scented oils on cotton balls, proprioceptive input will be provided with a 3 pound lap pad, vestibular input will be provided through written instruction of movement (walking, dancing, arm movements if unable to walk unassisted), and visual input via fiberoptic lights and a handheld liquid gel timer.

**Individualized Environmental Design Protocol:** Participants' caregivers will receive standard recommendations of physical environment modifications and caregiving techniques. Physical environmental modifications will include declutter living space, reduce background noise, increase natural light, accommodate for accessibility to commode and areas for drinking and eating. Caregiving techniques will include training for calming demeanor (emotional contagion), needs-driven care to decrease onset of behavioral disruption, and accepting and accommodating approach to behavioral disruption. Individualized sensory stimulation kits will be developed using subjects' preferred sensory stimuli (as determined by the Adult Sensory Profile assessment) and behavioral concerns identified in the COPM. One target behavior and/or time period of the day will be targeted for improvement. Selection of items included in the individualized sensory kit will be determined based on the attached decision tree and sensory mode plans. The sensory kit will be provided via caregiver administration or supervision two scheduled times (once in the morning and once in the afternoon) per day and one time as needed prior to activity or task associated with behavior concern to promote maintained behavioral regulation and adaptive responses.

**Data Analysis:** Due to the nature of feasibility of this study, sample size of 30 participants with cognitive impairment (10 per arm) does not fully power the study. Statistical description of behavior change results will be explorative and descriptive in nature. Per-protocol analysis (PPA) will be performed with 75% or more adherence to program as determined from weekly visits and journals. Power analyses for secondary outcome measures cannot be performed as this study is a preliminary investigation of these secondary outcome measures.

Summary statistics will be tabulated for the behavior change, protocol adherence, and adverse events. The frequencies of behavior change, protocol adherence, and adverse events will be compared between participants within same group and between group for differences.

Summary statistics will be tabulated by treatment arm for the baseline, week 4, and week 8 outcome measures of VABS, NPI, and protocol adherence based on behavior journals. The change from baseline to week 4 and follow-up will be calculated for each patient. Descriptive statistics will be examined to see whether levels of each assessment at baseline are normally distributed. If they are, then the mean changes will be compared in each treatment group with the standard of care group by analysis of variance (ANOVA). If they are not normal, then consideration will be given to data transformation.

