Once eligibility is confirmed, the research assistant will email a REDCap link to the caregiver for the Zarit Caregiver Burden and the Adult Sensory Profile, Actigraph and charger, and a copy of consent forms to the participant's caregiver. The PI will complete the COPM on visit 1, and provide caregiver and participant with Actigraph wear and care instructions. The VABS will be emailed to the caregiver via a confidential link through Pearson Publishing.

Subjects will be randomized to treatment arms by the statistical team. Participants will be randomized into one of the three groups: control, standard environmental design protocol, individualized environmental design protocol. Recruitment will be ongoing until all groups have 10 participants. In the event of drop out or early termination (causes will be recorded), researchers will recruit for replacement participants so that the study is completed with 30 entire study duration cases.

Visit 2 will consist of baseline assessment. A research assistant or the PI will complete the MOCA, with the participant with dementia. The caregiver will complete the NPI. Following Visit 2, an occupational therapist will be provided results of the COPM and ASP for participants of the individualized treatment arm. A sensory protocol will be developed based on assessment results following predetermined guidelines. All intervention materials for all study participants will be mailed to caregivers within 4 days of Visit 2. Upon receipt of intervention supplies, caregivers will contact the PI or occupational therapist for study initiation. Visit 3 will provide caregiver training for intervention use and initiation of Actigraph use. Adverse events since Visit 2 will be recorded. Visit 3 marks day 1 of intervention implementation. Participants will mail Actigraph back to UKADC in provided pre-paid envelop following week one of intervention.

Visits 4-8 will be scheduled at the end of each week following Visit 3. The PI, occupational therapist, or research assistant will record concurrent medication, and adverse events. With the caregiver, the interviewer will review behaviors observed by the caregiver, the behavior journal, compliance and acceptance of the intervention by the caregiver and the person with dementia. Actigraphs will be mailed from UKADC to participants, and patient will be asked to wear actigraph for last week of intervention window.

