Visit 9 will conclude the intervention window at the end of week 4. The PI, occupational therapist, research assistant will record adverse events, concurrent medication, Actigraph, and weekly behavior journals/compliance. The research assistant will conduct the NPI, COPM, VABS with the caregiver and the MOCA with the person with dementia. A member of the SBCoA medical team will conduct a physical and neurological exam. Due to the length of assessments within Visit 7, this session may be split and completed in more than one Zoom conference. The Zarit Caregiver Burden Scale will be emailed or mailed to the caregiver with prepaid envelop for return.

A four-week follow up will be conducted at Visit 10 whereby the research assistant will conduct the NPI, COPM, VABS with the caregiver, and the MOCA with the person with dementia. A member of the SBCoA medical team will conduct a physical and neurological exam. The Zarit Caregiver Burden Scale will be emailed or mailed to the caregiver with prepaid envelop for return.

Schedule of events can be found in attached detailed protocol.

A list of potential items sent in sensory kit is attached here.

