The investigator is responsible for retaining signed consent and assent documents and IRB research records for at least six years after study closure, as outlined in the Study Closure SOP [[PDF](#)]. If the research falls under the authority of the FDA or other regulatory agencies, or a study sponsor is involved, additional requirements may apply.

[Back to Top](#)

Each participant will be assigned a participant number and pseudonym, which will be used to identify the person during data analysis and when managing data. This de-identified human subject data will be stored on REDCap. Records maintained by SBCoA are not UK medical records, and so PHI and PII will not be used. At the conclusion of the study, all individual data will be stripped of identifying information and stored on REDCap, a secure location, for a period of 6 years, after which deletion of electronic files will destroy it. The IRB determined all video recording/electronic data must be destroyed using the University of Kentucky's Policy for Reuse and Disposal of Electronic Media. UK Healthcare Policy and Procedure A13-050 states "all electronic media shall be erased (i.e. purged) using data overwriting software that conforms to the requirements stated in NIST SP800-88." Confidentiality will be maintained, however, in the case in which abuse or concern of participants' safety, the researcher is required by law to report to authorities.

[Back to Top](#)

**Payment:** Describe the incentives (e.g., inducements) being offered to subjects for their time during participation in the research study. If monetary compensation is offered, indicate how much the subjects will be paid and describe the terms and schedule of payment. (It is IRB policy that provision should be made for providing partial payment to subjects who withdraw before the completion of the research. Monetary payments should be prorated or paid in full.)

No monetary incentive will be provided for participation in this study. Intervention kits will be mailed to participants for all arms of the study. These materials will not be returned to the researcher following study completion and kept by caregiver or patient, decided at their discretion.

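### The trial is labelled single-blind and placebo controlled, but active-versus-control comparisons on the caregiver-rated endpoints have neither a placebo nor blinding

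*Combined protocol and SAP*

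**What the plan says.** The study design text in the Research Description states: "This study will use a single-blind, placebo controlled, three-arm, parallel-design". It does not say who is blinded, how, or what the placebo is, and in the same paragraph it lists the first arm as standard care.

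The Control Group paragraph gives controls: "Standard of care for behavioral management and 2-page educational pamphlet describing safety for home environments". On kits it adds: "At the conclusion of the study, following the four-week follow up visit, participants will be offered a standardized sensory kit". The Payment section reads differently: "Intervention kits will be mailed to participants for all arms of the study". Research Procedures also has intervention materials going to every participant after Visit 2, without saying what controls are sent.

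On delivery, the Primary measures text says: "Caregivers will be responsible for providing treatment protocols throughout duration of treatment window". Research Procedures adds: "Visit 3 will provide caregiver training for intervention use and initiation of Actigraph use".

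On assessment, the Visit 9 text says: "The research assistant will conduct the NPI, COPM, VABS with the caregiver and the MOCA with the person with dementia". Visit 10 follows the same pattern, and Zarit is sent to the caregiver at both visits. For Visits 4-8: "The PI, occupational therapist, or research assistant will record concurrent medication, and adverse events". At those visits the interviewer also goes over the behaviour journal and compliance with the intervention.

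The Data Analysis text and the Statistical Analysis section both compare endpoints between arms. The Statistical Analysis section uses baseline-adjusted ANCOVA for secondary and exploratory endpoints and does not mention blinding.

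**The concern.** A placebo-controlled label tells the reader that expectation is balanced between arms. A single-blind label tells the reader that someone relevant to the outcome did not know the allocation. For the caregiver-rated endpoints, the documents describe neither protection. A caregiver who has been trained and has given a sensory kit daily for four weeks can hardly be unaware of being in an active arm, and a caregiver holding only a pamphlet can hardly believe otherwise. The same person then rates behaviour, function and their own burden.

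This bears on the study's aims. Objective 3 is behavioural impact, and behaviour change is listed with adherence under the primary feasibility measures. A reader who relies on the label would credit active-versus-control differences to the intervention with more confidence than the design supports. Adjustment for baseline does not help, because a rating shift that arises after randomisation and differs by arm is not in the baseline value. Multiple imputation addresses missing values, not biased ones.

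**Working it through.** The check is mainly a comparison of sections. The only design figure available is the sample size: 3 arms x 10 = 30, which agrees with the document. No alpha, effect size, SD or power is given for the behavioural endpoints, so there is no power calculation to reproduce.

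**Step 1: is there a placebo?** The design text claims one. That text and the Control Group paragraph define control as standard care plus a pamphlet. No section describes a sham kit or sham training. The Payment statement that kits go to all arms conflicts with the Control Group paragraph, but it does not describe a placebo either.

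**Step 2: who knows the allocation, and who rates?** That caregivers know is inferred from their training at Visit 3 and their role in delivery.

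| Measure after baseline | Source | Caregiver-rated? |
|---|---|---|
| NPI-Q | caregiver | yes |
| VABS | caregiver | yes |
| COPM | caregiver | yes |
| Zarit | caregiver | yes |
| Behaviour journal and adherence log | caregiver | yes |
| CDR | patient and informant, certified tester | partly |
| MoCA | patient | no |
| Actigraphy | device | no |

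Five of eight measures come wholly from the caregiver (62.5%), six of eight counting CDR (75%). Every behaviour scale is among the five. The session-completion endpoint in the Statistical Analysis section is not a rating.

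**Step 3: is there a masked interviewer?** The weekly compliance review is done by the principal investigator, the occupational therapist or a research assistant. A research assistant conducts NPI, COPM and VABS at Visits 9 and 10. Nothing separates the two duties, so the interviewer may know the arm. For VABS the described mode also changes, from an emailed caregiver link at baseline to a research assistant's interview at Visits 9 and 10.

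**Step 4: illustration of size.** The assumptions, none of them from the documents, are two-sided alpha 0.05, no true effect, and a shift b in active-arm ratings of 0.3 to 0.5 residual SD. With 10 per arm and ANCOVA on one baseline covariate, residual df = 30 - 3 - 1 = 26. For one active arm against control:

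- noncentrality = b^2 / (1/10 + 1/10) = b^2 / 0.2
- b = 0.3: 0.09 / 0.2 = 0.45
- b = 0.5: 0.25 / 0.2 = 1.25
- false-positive rate = P(F(1, 26; noncentrality) > 4.225) = 9.9% at b = 0.3 and 19.0% at b = 0.5

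A plain two-group t test with 18 df gives 9.7% and 18.5%. The result is about 10% to 19% in place of 5%.

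**The case against.** The strongest reply is that this is a labelling slip in a feasibility study. The design paragraph itself calls the comparator standard care, the Statistical Analysis section makes no blinding or placebo claim, and Data Analysis calls the behavioural results exploratory and not fully powered. This stands as a limit on consequence. It does not make the label correct.

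A second reply is that single-blind may refer to the person with dementia or to an assessor, and that the detailed protocol listed among the attachments, which is not in the file, may define it. This also stands. A reader might infer that nobody was masked, and the documents do not support that. But masking the patient or a MoCA tester would not blind the caregivers' ratings or turn a pamphlet into a placebo.

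Other stronger readings are tempting and should be resisted:

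- **All outcomes are compromised.** MoCA and actigraphy do not depend on the caregiver, CDR does so only in part, and session completion is not a rating.
- **NPI changes mode after baseline.** Research Procedures has the caregiver complete it at Visit 2, but Data Collection has it administered with the caregiver at all three time points, and no baseline NPI link is described. The change is documented for VABS only. Even there it is not beyond doubt, because the attached instrument is an interview form and Data Collection mentions a telehealth option.
- **Staff attention differs by arm.** The weekly visits are not restricted by arm, so contact may be similar. Training and kits are what differ.
- **Standard versus individualized is equally exposed.** Both arms receive kits and training, so a difference in expectation is much less clear.

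**Conclusion.** The contradiction stands on the documents' own text. The control is not a placebo, the masked party is not identified, and active-versus-control comparisons on NPI-Q, VABS, journal, COPM and Zarit have neither placebo control nor blinding. This rests on one inference: that caregivers trained in and delivering a kit know they are in an active arm.

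The size of any bias cannot be estimated from the documents. The 10% to 19% figure shows what an assumed shift of 0.3 to 0.5 SD would do at an assumed two-sided 5% level, and the conclusion does not depend on it. A reader might infer that the trial's results are invalid. That goes too far: the session-completion, MoCA and actigraphy endpoints do not rest on caregiver ratings, and the behavioural analyses are declared exploratory. The point should be corrected because it changes how the between-arm behavioural results may be read.

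**What to change.** 1. Delete the placebo claim and describe the trial as randomised and usual-care-controlled.
2. Limit single-blind to whichever party was actually masked, and say how the masking was kept. If no one was, remove the term.
3. Report NPI-Q, VABS, journal, COPM and Zarit as unblinded caregiver ratings, and interpret active-versus-control differences on them as possibly including expectation.
4. Reconcile the Payment statement on kits for all arms with the Control Group paragraph, and state what controls received and when.
5. Where still possible, collect VABS in the same mode at baseline, Visit 9 and Visit 10. This makes the measurements comparable but does not blind the caregiver.

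Items 1 to 4 cost only wording, and the price is a less favourable design label. Item 5 needs a small change of procedure. It may come too late, since the record is marked closed and the Statistical Analysis section is written in the past tense. In that case, report the modes used at each visit as a limitation.
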